6.1.3 Medical history

Medical history and ongoing medical conditions will be listed and summarized for the RS by study parts, treatment sequence, and for all participants by MedDRA SOC and PT. The reported term will be included in the listing. The summary will include the number and percentage of

study participants and will be sorted alphabetically by SOC and by descending incidence of PT within each SOC, based on the 'All Participants' column.

6.1.4 Meals and dietary restrictions

Study participants completion of High-fat High-calory breakfast at fed condition treatment period and compliance of fluid and meal restrictions during fasted condition treatment period will be listed.

6.1.5 Prior/concomitant medications

Medications with a start date prior to the first treatment will be considered as prior medications. Medications with a start date prior to, at or after the first treatment will be considered as concomitant medications if the duration overlaps at least 1 day with the any treatment period. Medications with a missing start date whose stop date is either unknown or after the date of the first treatment will be considered as concomitant.

Concomitant medications will be listed and summarized for the RS by study parts and treatment sequence, and will include WHODD (World Health Organization Drug Dictionary) Anatomical Main Group [Level 1 term text], Pharmacological Subgroup [Level 3 term text] and PT. The reported term will be included in the listing. Prior medications and concomitant medications will be summarized separately within the same table, ie, paged by prior and concomitant medications. Prior medications which continued into the study period are also classified as concomitant and are included in both summaries.

In the case of missing dates, the classification of medications as prior or concomitant will be performed after imputation of dates as described below. Imputations of missing dates will be performed prior to calculation of relative days.

The following rules are applied to impute partial start dates for medications:

- If only the month and year are specified and the month and year of first treatment is not the same as the month and year of the start date, then use the 1st of the month.
- If only the month and year are specified and the month and year of first treatment is the same as the month and year of the start date, then use the date/time of first treatment.
- If only the year is specified, and the year of first treatment is not the same as the year of the start date, then use January 1 of the year of the start date.
- If only the year is specified, and the year of first treatment is the same as the year of the start date, then use the date/time of first treatment.
- If the start date is completely unknown, then use the date/time of first IMP dose.

The following rules will be applied for partial stop dates and will be imputed for the calculation of duration of each medication:

- If only the month and year are specified, then use the last day of the month.
- If only the year is specified, then use December 31 of that year.
- If the stop date is completely unknown, do not impute the stop date.

Medications permitted to be continued during the study are limited to those listed in Section 6.5.1 of the protocol. No rescue medications are permitted.

All tabulations will be sorted alphabetically by Level 1 term, alphabetical Level 3 term within Level 1 and decreasing frequency of PT in the 'All Participants' column.

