5.5.2 Adverse Events

An Adverse Event is any untoward medical occurrence in a participant or clinical study participant, temporally associated with the use of study medication, whether considered related to the study medication.

Adverse events with start date/time prior to first treatment are defined as pre-treatment. These events will not be included in any tabulated summaries but will be listed.

Treatment emergent AEs (TEAE) are all AEs starting on or after the date/time of first treatment and up to including 4 days after last treatment, or any unresolved event already present before administration of treatment that worsens in intensity following exposure to the treatment.

AEs with a start date after 4 days of last treatment are defined as post-treatment. These events will not be included in any tabulated summaries but will be listed.

In case of missing or partially missing AE dates, the following rules will apply. Start and stop dates of AEs will be displayed as reported in the participant data listings (ie, no imputed values will be displayed in data listings).

The following rules will be applied for partial start dates and time:

- If only the month and year are specified and the month and year of the first treatment is not the same as the month and year of the start date, then use the 1st of the month, or the date of Screening if this is later (if the imputation results in an end date that is earlier than the start date, then use the 1st of the month). If time is missing, it will be imputed as 00:00 h
- If only the month and year are specified and the month and year of the first treatment is the same as the month and year of the start date, then use the date of the first treatment. If the imputed start date that is after the specified end date, then use the 1st of the month, or the date of Screening if this is later (if the imputation results in an end date that is earlier than the start date, then use the 1st of the month). If the imputed date is the date of treatment then time will be imputed as the start time of the treatment (ie, event will be regarded as treatment emergent)
- If only the year is specified, and the year of the first treatment is not the same as the year of the start date, then January 01 will be used. If time is missing, it will be imputed as 00:00 h

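### SAP 6.1.5 can set a medication's imputed start after its known pre-dose stop, so the record counts as neither prior nor concomitant

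*SAP*

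**What the plan says.** All the operative rules are in SAP 6.1.5.

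- **Prior** depends on the start date alone: "Medications with a start date prior to the first treatment will be considered as prior medications".
- **Concomitant** depends on overlap: a medicine is "considered as concomitant medications if the duration overlaps at least 1 day with the any treatment period".
- **Missing start:** one separate sentence covers medicines with no start date, but only those "whose stop date is either unknown or after the date of the first treatment will be considered as concomitant".
- **Order of steps:** "the classification of medications as prior or concomitant will be performed after imputation of dates as described below".
- **Start imputed as first dose:** this happens in three cases. A start with nothing known follows "If the start date is completely unknown, then use the date/time of first IMP dose". A start known to month and year takes the first dose if it falls in the dosing month; that rule ends "is the same as the month and year of the start date, then use the date/time of first treatment". A start known only to the year takes it when "the year of first treatment is the same as the year of the start date, then use the date/time of first treatment".
- **Start imputed earlier:** a start known to a different month goes to the first of that month, and a start known only to a different year goes to January 1 of that year.
- **Stop imputed late:** a stop known to the month goes to the last day of the month, and a stop known to the year goes to December 31. A wholly unknown stop is left missing.

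SAP 5.5.2 uses nearly the same start rules for adverse events, but adds a check against the end date, for example "If the imputed start date that is after the specified end date, then use the 1st of the month". SAP 6.1.6, on data derivation rules, is marked not applicable and adds nothing.

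**The concern.** Imputing the first dose suits a medicine that may have been running during treatment, because it errs towards concomitant. It does not suit a medicine known to have ended before dosing. There the stop date already proves that the start came earlier, and the imputed value contradicts a recorded date.

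Since classification uses imputed dates, the contradiction reaches the tables. The record cannot be prior, because its imputed start is not before first treatment. It cannot be concomitant, because it ended before any treatment period. It drops out of both summaries, and its derived duration and start day are wrong.

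At stake is the completeness of a descriptive table. Exclusion criterion 12 (Protocol 5.2) restricts medicines taken shortly before first dose, so recently stopped medicines are among those a reader would look for in the prior-medication summary.

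**Working it through.** The plan states no figure on this point, so there is none to reproduce. The check applies the SAP 6.1.5 rules literally to a set of start and stop patterns.

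**Inputs**
- Definitions, order of steps and imputation rules: SAP 6.1.5.
- Treatment periods: SAP Table 4. Treatment Period 1 is Day -1 to Day 1, Period 2 is Day 6 and Period 3 is Day 11.
- First dose: 15 Oct 2024. This date is an assumption for illustration only. Treatment Period 1 then begins on 14 Oct.

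**Tests**
- Prior: imputed start < 15 Oct 2024.
- Concomitant: the interval from imputed start to imputed stop shares at least one day with a treatment period.
- Duration difference: imputed stop minus imputed start, in days.

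| Recorded start | Recorded stop | Imputed start | Imputed stop | Stop minus start | Prior | Concomitant |
|---|---|---|---|---|---|---|
| Unknown | 5 Oct 2024 | 15 Oct | 5 Oct | -10 | No | No |
| Oct 2024 | 5 Oct 2024 | 15 Oct | 5 Oct | -10 | No | No |
| 2024 | 20 Aug 2024 | 15 Oct | 20 Aug | -56 | No | No |
| Unknown | Sep 2024 | 15 Oct | 30 Sep | -15 | No | No |
| Sep 2024 | 5 Oct 2024 | 1 Sep | 5 Oct | 34 | Yes | No |
| 2023 | 5 Oct 2024 | 1 Jan 2023 | 5 Oct | positive | Yes | No |
| Unknown | Oct 2024 | 15 Oct | 31 Oct | 16 | No | Yes |
| Unknown | Unknown | 15 Oct | none | not defined | No | Yes |
| Unknown | 14 Oct 2024 (Day -1) | 15 Oct | 14 Oct | -1 | No | Depends |

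The -56 is 11 days left in August, 30 in September and 15 in October.

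**Reading the table**
- The first four rows fail: start after stop, and neither class. In the first row the relative days would be Day 1 for the start and Day -10 for the stop.
- Rows five and six show the limit. A start known to an earlier month or an earlier year is handled correctly.
- Rows seven and eight show that a stop that is unknown, or partial in the dosing month, leads to concomitant and not to the gap.
- In the last row the answer turns on programming. If an interval that runs backwards counts as no overlap, the record is in neither class. If the code only compares endpoints, it is concomitant, because Treatment Period 1 begins on Day -1.

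**Effect of a guard.** Capping the imputed start at the stop date moves each of the first four rows to prior. The other rows keep their class, except the Day -1 stop, which becomes both prior and concomitant.

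**Can the 5.5.2 guard be copied?** Not for a wholly unknown start. There SAP 5.5.2 falls back to January 01 of the end year or, if later, the Screening date. With Screening on 8 Oct (again assumed; Day -7) and a stop on 5 Oct, the fallback start is 8 Oct, still after the stop.

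**The case against.** The best counter-argument is textual. SAP 6.1.5 sorts medicines with a missing start by their stop date. If imputed starts settled everything, that sentence would be largely redundant, so its author may have meant every other missing-start medicine to be prior. The inference is fair, but the SAP never states it, classification after imputation gives the opposite, and it helps partial starts less clearly.

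The other limits stand, and they rule out several stronger readings that a reader might draw.

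- **That every partial start is affected.** Two of the five start rules place the start in an earlier month or year, and those records remain prior.
- **That breaches of exclusion criterion 12 would be hidden.** That criterion turns on when use ended relative to first dose, not on the unknown start. Eligibility is verified at Screening and Day -1 (Protocol 1.3). Deviations, including eligibility and disallowed medication, are reviewed at data meetings (SAP 5.1.1.2 and 6.1.2). SAP 5.1 promises listings of all documented data, so the record and its stop date should still be visible.
- **That it will happen often.** No document says how often start dates are incomplete. At most 18 healthy participants are randomized and few medicines are allowed, so the count could be zero.
- **That ongoing medicines with an unknown start are lost.** They are still tabulated as concomitant. They miss only the second appearance, under prior, that 6.1.5 gives to continuing medicines. That is secondary.

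**Conclusion.** The point holds as an error in a stated rule. A medicine meets neither definition, and has a negative duration, when two conditions are both met:

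- its start is wholly unknown, or partial and in the month of first treatment (or in the year, if only the year is known);
- its stop, after its own imputation, falls before Treatment Period 1.

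A Day -1 stop is indeterminate.

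The effect is small. It touches the prior-medication summary and the derived duration and relative days. It does not touch the geometric mean ratios or their confidence intervals, and the listings should still carry the raw record. The conclusion assumes that the rules are programmed as written. The calendar dates in the check are illustrative, and the failure does not depend on them.

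**What to change.** Add two rules to SAP 6.1.5.

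1. If the imputed start falls after the stop date, reset it: to the first of the month when the month is known, to January 1 when only the year is known, and to a date no later than the stop when nothing is known. Do not carry over the Screening-date fallback from SAP 5.5.2, which can itself fall after the stop.
2. Class any medicine whose stop date is before first treatment as prior, whatever start was imputed.

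Under these rules the four failing patterns above get starts of 5 Oct or earlier, 1 Oct, 1 Jan 2024, and 30 Sep or earlier. All become prior with no negative duration.

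It would also help to say whether a stop on Day -1 counts as overlap with Treatment Period 1, so that the result does not depend on the code.

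The cost is two or three sentences in the SAP and a small programming change. No new data are needed.

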6.1.6 Data derivation rules

Not applicable.

6.1.7 AEs of Special Interest

AE of special interest are:

- Possible Hy's Law: Potential Hy's Law is defined as $\geq 3 \times \text{ULN}$, ALT or AST with coexisting $\geq 2 \times \text{ULN}$ total bilirubin in the absence of $\geq 2 \times \text{ULN}$ ALP, with no alternative explanation for the biochemical abnormality (ie, without waiting for any additional etiologic investigations to have been concluded).
- Hypersensitivity reactions (such as rash, angioedema, or anaphylaxis).

A listing will be produced of Potential Hy's Law for the SS by formulation and feeding condition.

A listing will be produced for Hypersensitivity reactions for the SS by formulation and feeding condition group using the following search strategy: Standardized MedDRA Queries (SMQ)='Hypersensitivity' (Broad) AND SMQ=Anaphylactic reaction (Broad).

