2.3 Benefit/risk assessment

This study will not provide a benefit to the study population, ie, healthy study participants. This study will provide relevant PK and clinical safety information to support minzasolmin new tablet formulation development.

A summary of possible risks and adverse reactions is provided in the IB based on a review of adverse event (AE) data from 98 study participants exposed to minzasolmin in completed clinical studies UP0030 (51 participants), TM0017 (4 participants), UP0077 (21 participants), and UP0078 (22 participants), and based on the review of safety data in the ongoing clinical studies UP0073 (42 participants), and PD0053 and its extension study PD0055 conducted in approximately 490 participants (from PD0053).

Overall, the majority of treatment-emergent adverse events (TEAEs) observed in clinical studies with minzasolmin to date were mild or moderate in intensity and resolved. In UP0030, 2 events of hypersensitivity were reported. An additional 2 events of hypersensitivity occurred in study participants who received minzasolmin in UP0077. A causal relationship between the reported events of hypersensitivity and minzasolmin is considered plausible. Hypersensitivity reactions are considered an important identified risk for minzasolmin and are further described in the IB.

There have been no reports of anaphylaxis in the minzasolmin clinical program.

Of all the adverse drug reactions reported in completed minzasolmin clinical studies, based on the frequency of occurrence, all are considered common ($\geq 1\%$ and $< 10\%$).

In the ongoing Phase 2 study (where participants are receiving daily doses of Study Drug for 18 months), of the 496 participants, 8 reports of aspartate aminotransferase (AST) and/or alanine transaminase (ALT) elevations > 3 times upper limit of normal (ULN) (of which 2 were > 10 times ULN)

have been received. In the majority of reports, the transaminase elevations were noted 2 to 3 months after the first dose of study medication. None of the reports had an increase in bilirubin or international normalized ratio (INR) and none met Hy's law criteria. Transaminase values decreased spontaneously without study drug discontinuation in 3 participants or after discontinuation of the drug in 5 participants.

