8.4.6 Adverse events of special interest

An adverse event of special interest (AESI) is any AE that a regulatory authority has mandated be reported on an expedited basis, regardless of the seriousness, expectedness, or relatedness of the AE to the administration of a UCB product/compound or associated medical device. For minzasolmin, the following events require immediate reporting (within 24 hours regardless of seriousness) to UCB:

- Possible Hy's Law (as per Section 7.1.1)
 - Potential Hy's Law, defined as $\geq 3 \times \text{ULN}$, ALT or AST with coexisting $\geq 2 \times \text{ULN}$ total bilirubin in the absence of $\geq 2 \times \text{ULN}$ ALP, with no alternative explanation for the biochemical abnormality (ie, without waiting for any additional etiologic investigations to have been concluded). Follow up information should be reported if an alternative etiology is identified during investigation and monitoring of the participant.

- Hypersensitivity reactions (such as rash, angioedema, or anaphylaxis)

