A by-participant listing will be presented for by formulation and feeding condition for all AEs for the SS. This will include reported term, SOC, PT, the onset date/time and outcome date/time

of the event (including relative days), stop date and time (or ongoing, if applicable; relative days), the AE duration, severity, relationship, action taken, and outcome. In addition, the listing will flag TEAEs, Serious TEAEs, and AE of special interest. A glossary of AE terms including reported term, SOC and PT will also be presented.

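### The hypersensitivity listing in SAP 6.1.7 joins its two SMQs with AND; coded literally, it leaves out any event found by only one of them

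*SAP*

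**What the plan says.** Protocol 8.4.6 names two AESIs for minzasolmin. One is potential Hy's Law; the other is "Hypersensitivity reactions (such as rash, angioedema, or anaphylaxis" and the like. SAP 6.1.7 repeats that definition with the same scope.

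For output, SAP 6.1.7 states: "A listing will be produced for Hypersensitivity reactions for the SS by formulation and feeding condition group using the following search strategy". The strategy that follows names the Hypersensitivity SMQ and the Anaphylactic reaction SMQ, both broad, connected as "Broad) AND SMQ=Anaphylactic reaction (Broad". The SAP does not say that AND means running both queries and pooling the results. It also does not say whether the second query is used as a plain term list or by its algorithm.

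SAP 5.5.2 adds that in the by-participant listing of all AEs "the listing will flag TEAEs, Serious TEAEs, and AE of special interest". It gives no derivation for the AESI flag. The TEAE summaries named in that section include no AESI table, so the listing in 6.1.7 is the only output dedicated to hypersensitivity.

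On background, Protocol 2.3 says: "Hypersensitivity reactions are considered an important identified risk for minzasolmin". It gives the history as "In UP0030, 2 events of hypersensitivity were reported" and "An additional 2 events of hypersensitivity occurred in study participants who received minzasolmin in UP0077", and adds "There have been no reports of anaphylaxis in the minzasolmin clinical program".

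**The concern.** The definition is met by any one manifestation. The search, read as a Boolean expression, asks an event to satisfy two conditions at once. An intersection cannot be larger than either of the queries that form it, so the listing can be narrower than the category it is meant to display.

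Hypersensitivity is the reaction that the protocol singles out as an identified risk. An incomplete listing could be read in the study report as the full account of such events by formulation and feeding condition. It could also disagree with what the site sent to the sponsor: Protocol 7.1.4 has a possible hypersensitivity reaction reported as an AESI on the SAE form, and the SAP has no rule that carries those reports into the listing.

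**Working it through.** The plan states no figure for this point, so there is nothing to reproduce. The check is one of set logic.

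**Inputs**
- H: events returned by the Hypersensitivity SMQ, broad (SAP 6.1.7).
- A: events returned by the Anaphylactic reaction SMQ, broad (SAP 6.1.7).
- Operator as written: a capitalised AND (SAP 6.1.7).
- Target: hypersensitivity reactions, with the manifestations given as alternatives joined by or (Protocol 8.4.6; SAP 6.1.7).

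**What each rule returns**

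| Event is found by | As written: H AND A | With OR: H OR A |
|---|---|---|
| both queries | listed | listed |
| H only | left out | listed |
| A only | left out | listed |
| neither | left out | left out |

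**Reasoning**
1. Events lost by the written rule are those in H only plus those in A only.
2. That loss is empty for every possible dataset only if H and A are the same query. In that case there would be no reason to name two.
3. An event found by the Hypersensitivity SMQ alone is a candidate for the AESI as defined, because the definition does not require anaphylaxis. The written rule removes it; the union keeps it.
4. An event found by the Anaphylactic reaction SMQ alone is likewise a candidate, because anaphylaxis is one of the named examples. The written rule removes that too.
5. The union therefore matches the definition and the intersection does not.

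**What cannot be worked out**

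The documents do not reproduce the SMQ term lists. What the second query returns depends on those lists and on whether it is applied as a list or by its algorithm. Neither the size of the H-only and A-only groups nor their content can be obtained from the documents.

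**Where the error travels**
- The hypersensitivity listing: affected directly.
- The AESI flag in the all-AE listing: affected only if it is built from the same search, which SAP 5.5.2 leaves open.
- The listing of all AEs and the TEAE tables by SOC, HLT and PT: not affected.
- The secondary safety endpoints (TEAEs, serious TEAEs, TEAEs leading to withdrawal) and all PK analyses: not affected.

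**The case against.** **AND may be loose English.** The sentence names two queries under the label of a search strategy and may simply mean that both are to be run. This is possible, and the definition beside it supports that intent. But the text does not say so, and a capitalised operator between two query conditions invites a programmer to code an intersection. If pooling was meant, the wording still needs correcting.

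**Nothing is hidden.** All AEs are listed by participant, AESIs are flagged there, TEAEs are tabulated, and possible hypersensitivity reactions go to the sponsor on an expedited basis. With at most 18 participants, a reader can inspect every event. This stands, and it limits the harm. It does not make the rule correct.

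**A particular loss is not shown.** A reader might infer that isolated rash, or the non-anaphylactic kind of event seen so far in the programme, will be dropped. The documents do not support that. The absence of anaphylaxis as a diagnosis does not show that a given skin term lies outside a broad anaphylaxis query. The anaphylaxis criteria in Protocol 8.4.6.1.1.1 are clinical criteria, not the SMQ. This objection stands in full.

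**A probability is tempting but would mislead.** Protocol 2.3 gives 2 + 2 = 4 events among 98 exposed participants. Treating each event as one participant, the chance of at least one in 18 is 1 − (1 − 4/98)^18 = 0.53. Using only the two studies with events (51 + 21 = 72 participants), it is 1 − (1 − 4/72)^18 = 0.64. Both describe the chance that an event occurs, not that one is omitted. The rates come from studies that included multiple dosing (Protocol 4.3), whereas this study gives three single doses and excludes people with relevant allergy (Protocol 5.2, criterion 7). The denominator of 72 is also chosen because those studies had events. Neither figure measures the size of this problem.

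**Conclusion.** Wrong as written, with impact limited to a safety listing. The literal rule is an intersection, while the definition in the same section calls for a union. Any event found by only one query would be missing from the dedicated hypersensitivity listing, and from the AESI flag if that flag uses the same search.

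The conclusion rests on two things: AND being coded as a Boolean operator, and the two queries not being identical. It does not rest on any particular term being lost, or on any rate of hypersensitivity. The logic is firm; how many events would be lost in practice, if any, is unknown from the documents.

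**What to change.** In SAP 6.1.7:
- Replace AND with OR, so that the listing is the union of the two broad SMQs.
- State whether the Anaphylactic reaction SMQ is applied as a term list or by its algorithm.

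In SAP 5.5.2, state that the AESI flag for hypersensitivity follows the same rule, so that the two listings agree.

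Optionally, reconcile the result with the events that the investigator reported as hypersensitivity AESIs and list any that the search did not find. This is extra data handling and is not needed to correct the error.

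The operator change is one word. With the two clarifications it is a short SAP edit and a matching program change. The downside is a possibly longer listing in a study of at most 18 participants. Nothing in study conduct or clinical management changes.
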